- 1b) to prospectively assess the potential clinical impact of HRME on the diagnosis and endoscopic surveillance of BE-associated neoplasia by determining if HRME alters the decision to obtain a mucosal biopsy or perform endoscopic mucosal resection (EMR) and changes the total number of total mucosal biopsies taken per procedure;
- 2) to determine the diagnostic accuracy (sensitivity, specificity, positive predictive value, negative predictive value) of HRME for the in-vivo diagnosis of neoplasia in a surveillance population of patients with BE using histopathologic diagnosis of mucosal biopsies as the reference standard;
- 3) to compare the total procedure time for imaging and mucosal biopsy acquisition of HRME with WL, stratified by length of BE (less than 3 cm and greater than 3 cm) and to determine the average HRME imaging time.

Section E: Protocol Risks/Subjects

E1. Risk Category

Category 3: Research involving greater than minimal risk and no prospect of direct benefit to the individual subject, but likely to yield generalizable knowledge about the subject's disorder or condition.

E2. Subjects

Gender:

Both

Age:

Adult (18-64 yrs)

Ethnicity:

All Ethnicities

Primary Language:

English

Groups to be recruited will include:

Patients

Which if any of the following vulnerable populations will be recruited as subjects?

Vulnerable populations require special protections. How will you obtain informed consent, protect subject confidentiality, and prevent undue coercion?

E3. Pregnant woman/fetus

Will pregnant women and/or fetuses (as described in 45 CFR 46 Subpart B) be enrolled in the research?

No

E4. Neonates

Will neonates of uncertain viability or nonviable neonates (as described in 45 CFR 46 Subpart B) be enrolled in the research?

No

E5. Children

Will children be enrolled in the research?

No

Section F: Design/Procedure

F1. Design

Select one category that most adequately describes your research:

u) Drug, Phase II, Single Center

Discuss the research design including but not limited to such issues as: probability of group assignment, potential for subject to be randomized to placebo group, use of control subjects, etc.

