All patients who fit the study criteria will be consented for HRME with biopsy and possible EMR (similar to colonoscopy with possible polypectomy). Examination of the esophagus, stomach, and small intestine with standard endoscopy will be performed using a high resolution video endoscopy (Olympus). The level of the gastroesophageal (GE) junction will be recorded. The level of the squamo-columnar junction (Z line) will also be recorded. Any proximal displacement of the Z line or gap between the GE junction and Z line will normally raise the suspicion for BE due to the presence of columnar mucosa in the distal esophagus. The maximum length of suspected BE (i.e. distance between the GE junction and Z line) and pattern of the BE (islands, tongues, circumferential columnar epithelium) will be recorded and photographed. A description of the BE using the Prague C&M criteria, which is used to describe the maximal length of BE and extent of circumferential BE, will also be recorded {Sharma, 2006 #4178}. Esophagitis will be described using the Los Angeles classification. The size, morphology, and location in the esophagus of every macroscopically visible lesion will be recorded and described using the 2002 Paris Endoscopic Classification of neoplastic lesions. The height of the mucosal lesion will be assessed by comparison with the diameter of a closed biopsy forceps (2.5 mm) {, 2003 #4280}.

After the endoscopic examination, the endoscopist will provide an endoscopic diagnosis for any visible mucosal lesions (pre-HRME diagnosis: i.e. neoplastic vs. non-neoplastic) and a plan for management during the procedure, such as biopsy or endoscopic mucosal resection (pre-HRME plan). These will be recorded prior to the initiation of HRME imaging.

For the HRME portion of the exam, 5-10 ml of proflavine hemisulfate (0.01%) will be sprayed on the esophageal mucosa. Proflavine is being used under an IND from the FDA (#102217). The HRME itself is an IDE exempt device per the FDA. The HRME will then be inserted through the biopsy channel of the endoscope and gently placed against the mucosa. The endoscopist will image each WL-discrete lesion first from the most distal to the most proximal. For each HRME imaged site, an optical read will be obtained (neoplastic vs. non-neoplastic) followed by a tissue biopsy of the imaged areas.

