There may be potential benefit to the individual participant for undergoing HRME as dysplasia may be identified by the procedure. All medical management decisions will be based upon the standard endoscopic and pathologic diagnoses.

Describe potential benefit(s) to society of the planned work.

The original purpose of this research was to provide a low-cost, portable endoscopic tool that can advance the screening of esophageal adenocarcinoma in BE patients. As incidence rates for cancer rise, it is imperative that we improve early detection strategies. More importantly, it is critical that we develop cost-effective, robust platforms that can be used in community based screening/ surveillance programs. We believe that successful results can be translated to other organ systems and, thus, help address the global costs of rising cancer incidence

Do anticipated benefits outweigh potential risks? Discuss the risk-to-benefit ratio.

The incremental risks of HRME with proflavine, added to the SOC white light with Lugol's iodine are minimal. White light endoscopy is standard of care and all subjects will be undergoing this SOC procedure.

Section J: Consent Procedures

J1. Waiver of Consent

Will any portion of this research require a waiver of consent and authorization?

Yes

Please describe the portion of the research for which a waiver is required. (Example: chart review to determine subject eligibility)

We will screen gastroenterology and endoscopy clinic schedules at BSLMC to identify current patients who may be eligible for participation in our clinical trial. Eligible subjects approved by a GI physician will then be contacted via telephone to determine participation interest, followed up by written, in-person consent prior to the procedure.

Explain why the research and the use or disclosure of protected health information involves no more than minimal risk (including privacy risks) to the individuals.

We will only store minimally required information on individuals who meet our inclusion and exclusion criteria. This information will be stored electronically behind BCM's firewall, and only research staff on a need to know basis will have access to the list. We don't believe this chart review will present additional privacy risk beyond routine patient care including use of electronic medical records.

Explain why the waiver will not adversely affect the privacy rights and the welfare of the research subjects.

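### Aim 1b: as written, Group B cannot show that HRME changed the biopsy decision, because no post-HRME plan is recorded and a biopsy follows every optical read

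*Protocol*

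**What the plan says.** **The aim.** Protocol, Section D, aim 1b sets out to assess the potential clinical impact of HRME "by determining if HRME alters the decision to obtain a mucosal biopsy or perform endoscopic mucosal resection (EMR") and by seeing whether it "changes the total number of total mucosal biopsies taken per procedure". That makes three parts: the biopsy decision, the EMR decision and the biopsy count.

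**Before imaging, Group B (Section F2).** After the white-light examination "the endoscopist will provide an endoscopic diagnosis for any visible mucosal lesions", together with "a plan for management during the procedure, such as biopsy or endoscopic mucosal resection (pre-HRME plan"). On timing: "These will be recorded prior to the initiation of HRME imaging".

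**During imaging, Group B (Section F2).** At each lesion seen on white light, "an optical read will be obtained (neoplastic vs. non-neoplastic) followed by a tissue biopsy of the imaged areas". Flat Barrett's mucosa is then biopsied at random in four quadrants, every 1 cm or every 2 cm, with an HRME read before each biopsy. No post-HRME plan is mentioned in either document.

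**Group A (Section F2).** Discrete lesions are biopsied, and flat mucosa gets four-quadrant biopsies every 1 cm or every 2 cm.

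**Elsewhere.** Section D (aim 1a) and Section F1 describe Group B as HRME with directed biopsy. Section I states: "All medical management decisions will be based upon the standard endoscopic and pathologic diagnoses". Section G2 of the Protocol, repeated in the SAP, specifies diagnostic yield and specificity. It gives no endpoint or analysis for aim 1b.

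**The concern.** To show that a test altered a decision, one needs the decision before the test and the decision after it. F2 collects the first, for visible lesions, but not the second. What it collects after imaging is a binary optical read. A read is a diagnosis. It does not say whether the endoscopist would have left the site alone, biopsied it or resected it. F2 itself keeps diagnosis and plan apart in the pre-HRME record.

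The action cannot stand in for the missing plan, because no rule lets a non-neoplastic read cancel a biopsy or a neoplastic read add one. What is at stake is the claim that motivates the study: Section C argues that areas read as non-neoplastic might be left without biopsy. Aim 1b is where the trial would test whether endoscopists would act on that. An intended plan that is not written down at the time cannot be validly reconstructed afterwards.

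**Working it through.** **1. The plan's own figure.** None is given for aim 1b. The only sample-size arithmetic in Section G1 is 50 × (1 − 0.20) = 40 completers per arm. It reproduces at the 20% end of the stated range (15% would give 42.5) and has no bearing on this point.

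**2. Each part of the aim against the data F2 collects in Group B.**

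| Part of aim 1b | Known before HRME | Known after HRME | Is the action fixed? | What can be shown |
|---|---|---|---|---|
| Biopsy, visible lesion | Diagnosis and plan | Optical read | Yes, biopsy follows | Change of diagnosis, not of decision |
| Biopsy, flat site | Four-quadrant biopsy, set by protocol | Optical read | Yes, biopsy follows | No decision; only a hypothetical count |
| EMR, visible lesion | Plan | EMR done or not, from resected specimens | No | Planned against performed, without a reason for change |
| Flat-mucosa biopsy count | – | Biopsies taken | Yes, same scheme as Group A | Prescribed difference of 0 at equal spacing |

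**3. Flat-mucosa biopsies prescribed.** With segment length L and spacing s, and assuming a biopsy level at the GE junction itself, n = 4 × (⌊L/s⌋ + 1). The lengths are illustrative; eligibility requires more than 1 cm and sets no upper limit.

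| L | s = 2 cm: A, B | s = 1 cm: A, B | Difference, B − A |
|---|---|---|---|
| 2 cm | 8, 8 | 12, 12 | 0 |
| 4 cm | 12, 12 | 20, 20 | 0 |
| 6 cm | 16, 16 | 28, 28 | 0 |
| 8 cm | 20, 20 | 36, 36 | 0 |

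**4. A count difference that is not due to HRME.** The trigger for 1 cm spacing is suspected neoplasia in Group A but suspected high-grade dysplasia in Group B. If a patient with a 6 cm segment met the first trigger but not the second, the prescribed counts would differ by 28 − 16 = 12 biopsies according to arm. For a 4 cm segment the gap is 20 − 12 = 8. Neither gap has anything to do with the optical read.

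**5. What the reads alone could give.** Take the pilot sensitivity of 81% and specificity of 85% (Section C) and assume a site-level neoplasia prevalence p of 1% to 20%. The share of sites read non-neoplastic is p × (1 − 0.81) + (1 − p) × 0.85.

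- p = 0.01: 0.0019 + 0.8415 = 0.843
- p = 0.20: 0.0380 + 0.6800 = 0.718

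Of 12 flat sites, that is 12 × 0.843 = 10.1 down to 12 × 0.718 = 8.6 non-neoplastic reads. Under F2 the number of biopsies omitted is 0. These reads become biopsies spared only if every non-neoplastic read is taken to mean no biopsy, which the documents neither state nor test.

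**The case against.** A reader might infer that aim 1b cannot be answered at all. The documents do not support that. The aim is framed as potential impact, and three kinds of indirect evidence exist. F2 does not fix EMR: patients consent to possible EMR, a plan that may name EMR is recorded, and resected specimens go to pathology, so planned and performed EMR can be compared. The pre-HRME lesion diagnosis and the optical read share one scale (neoplastic or not), so a change of diagnosis can be tabulated. Non-neoplastic reads can be counted. All of this stands, but none of it is a record of an altered biopsy decision.

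A reader might also infer that the observed change in biopsy decisions must be zero. That goes too far for lesions. If the pre-HRME plan was not to biopsy, the mandated biopsy makes plan and action differ. That difference is forced by the protocol and says nothing about HRME, but it is not zero.

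Nor does flat mucosa lack a starting plan. The endoscopist records none, but the protocol sets it: four-quadrant biopsy. Only the plan after imaging is missing there.

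Two further objections have weight. Section I is weak support on its own: it does not say whether medical management includes biopsy or EMR during the procedure, and it refers to Lugol's iodine, which F2 never mentions, so its wording may not be specific to this trial. And if the word directed in aim 1a and Section F1 governs rather than the F2 steps, biopsy decisions and counts in Group B could be real outcomes. That is a reason to reconcile the passages. It does not remove the gap, because the F2 steps are the only operational description of Group B.

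Finally, aim 1b is neither the primary outcome nor the secondary outcome named in Section G2. That limits the severity of the point, not its truth.

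**Conclusion.** The point holds in a limited form. Run as F2 is written, the trial cannot show that HRME changed the decision to biopsy. At equal spacing, the prescribed flat-mucosa count is the same in both arms, a difference of 0 at every segment length tried. On EMR the evidence is indirect: planned against performed, with no post-HRME plan and no reason recorded. The total count per procedure may still differ between arms, for instance through the two triggers for 1 cm spacing or the number of samples per lesion, but such a difference could not be credited to HRME.

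The conclusion rests on reading the F2 steps as the operative description of Group B. The biopsy counts also assume a level at the GE junction and illustrative segment lengths; the difference of 0 depends only on the arms using the same scheme and spacing. The matter should be corrected because it affects a stated aim. It does not touch the primary analysis.

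**What to change.** **Record.** In Group B, at every imaged site, after the optical read and before tissue is taken, record the endoscopist's intended post-HRME plan: biopsy, no biopsy or EMR. At lesions, compare it with the pre-HRME plan already recorded. At flat sites, compare it with the protocol-set four-quadrant biopsy; no extra pre-HRME field is needed there. Only an intention is recorded, so no patient's biopsies or care change.

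**Define and analyse.** State that aim 1b concerns intended decisions. Add to Section G2 and the SAP:

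- the proportion of sites and the proportion of patients whose plan changed;
- the number of biopsies intended under the post-HRME plan, set against the number taken;
- a method for site-level results that allows for correlation within patients, stratified by risk group as G2 requires of all analyses.

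**Reconcile.** Three sets of passages must be brought into line; no position is taken here on which rule is right:

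- directed biopsy for Group B (Section D aim 1a, Section F1) against random four-quadrant biopsy in Group B (Section F2);
- the different triggers for 1 cm spacing in the two arms (Section F2);
- the statement on management in Section I, which should say whether it covers biopsy and EMR during the procedure.

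**Cost.** One field per site, a short protocol addition and a few seconds per site in one arm. At an assumed 5 to 10 seconds, 12 flat sites add 12 × 5 = 60 to 12 × 10 = 120 seconds. Aim 3 compares procedure time between arms, so this recording should be timed separately or excluded from that comparison. Section H1 lists added sedation time as a risk, so the entry should be kept brief.

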Preliminary ex-vivo data has been published in *Gastrointestinal Endoscopy*. This data confirmed that HRME images of Barrett's metaplasia and neoplasia could be correlated to gold standard histopathology. Moreover, our group recently conducted a small pilot study of HRME in a high risk BE population that demonstrated a sensitivity of 81% and a specificity of 85%. Most encouraging, however, was the negative predictive value of 95% that we achieved in this study. This suggests that areas that are deemed "non-neoplastic" on HRME may not need to be biopsied.

We believe that the next step in determining whether HRME can enhance the efficiency and yield of current surveillance is to perform a randomized, controlled trial comparing HRME to standard white light endoscopic protocol. Moreover, the in-vivo data we hope to collect will show that HRME will allow endoscopists to make informed real-time decisions regarding biopsies and endoscopic mucosal resections. Ultimately, we believe HRME can reduce the number of biopsies necessary as well as the total procedure time required to screen for BE-associated dysplasia and EAC. Therefore, HRME could reduce the overall cost of screening and become a much more attractive option for low-income communities.

As incidence rates for cancer rise, it is imperative that we improve early detection strategies. More importantly, it is critical that we develop cost-effective, robust platforms that can be used in community based screening/surveillance programs. We believe that successful results can be translated to other organ systems and, thus, help address the global costs of rising cancer incidence.

Section D: Purpose and Objectives

Our central hypothesis is that the low-cost HRME will increase the efficiency and yield of the current standard of endoscopic surveillance of BE. We believe the HRME will provide an in-vivo "optical biopsy" that will be comparable to gold standard histopathology and allow the endoscopist to make a more informed decision about whether to obtain a biopsy or even perform endoscopic therapy (i.e. endoscopic mucosal resection, EMR). Specific aims of this project are, in patients with known BE:

- 1a) to compare the diagnostic yield (defined as the proportion of mucosal biopsy samples with neoplasia) of HRME with directed biopsy to standard white-light endoscopy with 4-quadrant random biopsy (WL) for the diagnosis of BE-associated neoplasia in flat mucosa as well as mucosal lesions;

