The patient will be assigned to one of two groups: Group A: high resolution white-light endoscopy followed by random biopsy (WL) or Group B: high resolution white-light endoscopy plus HRME followed by directed mucosal biopsy (HRME). Randomization assignments (WL vs. HRME) will be computer-generated with allocation concealment using sealed envelopes.

Inclusion Criteria:

All consecutive outpatients with > 1 cm biopsy-proven Barrett's Esophagus who are undergoing standard of care endoscopic surveillance for metaplasia, dysplasia, or neoplasia.

Exclusion Criteria:

- Allergy or prior reaction to the fluorescent contrast agent proflavine
- Patients who are unable to give informed consent
- Known advanced adenocarcinoma of the distal esophagus, or dysplastic/suspected malignant esophageal lesion greater than 2 cm in size not amenable to EMR
- Patients with a history of a severe allergic reaction (anaphylaxis)
- Patients unable to undergo routine endoscopy with biopsy
- Women who are pregnant or breastfeeding
- Prothrombin time greater than 50% of control; PTT greater than 50 sec, or INR greater than 2.0
- Inability to tolerate sedated upper endoscopy due to cardiopulmonary instability or other
- Patients with known, untreated esophageal strictures, prior partial esophageal resection, or altered anatomy preventing passage of the endomicroscope
- Patients with known severe esophagitis
- Patients with suspected but no biopsy confirmed BE

F2. Procedure

Written informed consent will be obtained prior to study participation using the IRB-approved consent form. Identifying information collected includes D.O.B., age, gender, race and date of encounter. The patient will be assigned to one of two groups: Group A: high resolution white-light endoscopy followed by random biopsy (WL) or Group B: high resolution white-light endoscopy plus HRME followed by directed mucosal biopsy (HRME). Randomization assignments (WL vs. HRME) will be computer-generated with allocation concealment using sealed envelopes.

White Light Endoscopy (WL) Procedure (Group A)

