Patients assigned to the WL group will undergo careful standard examination of the upper GI tract with a standard high resolution endoscope (Olympus Corporation) without HRME. Endoscopic landmarks and BE characteristics will be described as listed in the previous section. Any mucosal lesions in the BE will be classified using the Paris classification. The endoscopist will predict whether BE and dysplasia are present based upon the white light endoscopic findings (endoscopic diagnosis) and whether neoplasia is suspected if there are any endoscopic lesions (endoscopic plan).

Mucosal biopsies of any discrete lesions will be obtained and placed in separate pathology containers per standard of care. Then, four-quadrant mucosal biopsies of the flat BE mucosa (a biopsy from each quadrant of the BE at each level) will be taken per standard of care: every 1 cm (for patients with suspected neoplasia) or every 2 cm (for patients undergoing routine surveillance), starting at the GE junction, moving proximally to the squamocolumnar junction. These mucosal biopsies will be obtained in a similar fashion to the standard Seattle biopsy protocol⁴. This biopsy protocol is commonly used for obtaining surveillance biopsies to sample representative areas of the entire length of the BE. Each level of the biopsies designated by the distance (in centimeters) on the endoscope from the patient's gums.

The total time of the procedure, as well as the time needed to complete the standard endoscopy and the time needed to take tissue biopsies, will be recorded. The co-investigator or research coordinator will indicate the biopsy number and location of the biopsy on a standardized BE map. The biopsies from each site will be placed in formalin and labeled according to the biopsy location.

Post-procedure, the endoscopist will inspect the map created by the coordinator and approve the data recorded. The number of biopsies obtained and biopsy specimen bottles sent for processing will be tracked to allow calculation of pathology costs.

High Resolution Microendoscopy (HRME) Procedure (Group B)

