Following the targeted biopsies, random four-quadrant biopsies of the flat BE mucosa will be taken with every 1 cm (for patients with suspected high grade dysplasia (HGD)) or every 2 cm (for patients undergoing routine surveillance), starting at the GE junction, moving proximally to the Z line per standard of care. Prior to the standard tissue biopsy, an HRME read will be obtained from the area (neoplastic vs. non-neoplastic). A superficial dimple will be made with the HRME of each imaged site to "mark" the imaged area for biopsy. The latter is commonly performed in imaging correlation studies and has not been shown to affect pathology.

Pathology

The fixed biopsies will be oriented/embedded in paraffin and sectioned to facilitate comparison between histology and HRME images. Afterwards the serial sections will be routinely stained with hematoxylin and eosin for histopathologic examination.

The biopsies or resected specimens (from EMR) obtained from the examined areas will be routinely processed and interpreted by a single expert gastrointestinal pathologist in a blinded fashion and graded according to the Vienna Classification. The pathologist will provide a diagnosis for each biopsy specimen in the cassette to allow correlation with the endoscopic and HRME findings. The histopathologic diagnosis for each biopsy will be recorded on a standardized data collection form.

Section G: Sample Size/Data Analysis

G1. Sample Size

How many subjects (or specimens, or charts) will be used in this study?

Local: 47 Worldwide: 100

Please indicate why you chose the sample size proposed:

Approximately 100 subjects with 50 in the WL-arm and 50 in the HRME-arm. We anticipate that 15-20% of subjects may be not complete their endoscopy for various reasons (lack of biopsies, loss of Barrett's mucosa, visualization of a lesion > 2 cm, inability to complete endoscopy, etc.) which would allow 40 in each arm. Since each patient only requires one visit for enrollment into the study, we expect that 80 patients will be enrolled and randomized and complete the study.

G2. Data Analysis

Provide a description of your plan for data analysis. State the types of comparisons you plan (e.g. comparison of means, comparison of proportions, regressions, analysis of variance). Which is the PRIMARY comparison/analysis? How will the analyses proposed relate to the primary purposes of your study?

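### Group B is labelled HRME-directed biopsy, but its procedure takes essentially the same tissue as Group A whatever the read, so the primary all-biopsies contrast cannot test directed biopsy

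*Protocol*

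**What the plan says.** **The label.** Aim 1a (Protocol, Section D) compares the yield of "HRME with directed biopsy to standard white-light endoscopy with 4-quadrant random biopsy (WL"). F1 and F2 repeat the label: "Group B: high resolution white-light endoscopy plus HRME followed by directed mucosal biopsy (HRME"). Section C gives the reasoning: areas called non-neoplastic "on HRME may not need to be biopsied", and ultimately "HRME can reduce the number of biopsies necessary as well as the total procedure time required". Aim 1b asks whether HRME alters the decision to biopsy or resect and "changes the total number of total mucosal biopsies taken per procedure".

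**The procedure.** In F2, Group B, each lesion seen on white light is imaged, read as neoplastic or not, and then biopsied. Next: "Following the targeted biopsies, random four-quadrant biopsies of the flat BE mucosa will be taken", with a read recorded before each standard biopsy. F2, Group A, also biopsies every discrete lesion and then takes four-quadrant biopsies. The one stated difference in sampling is the trigger for 1 cm rather than 2 cm spacing: suspected neoplasia in Group A, suspected high-grade dysplasia in Group B.

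**The analysis.** G2 (Protocol and SAP, same text) defines diagnostic yield as the share of all biopsies confirmed as neoplastic. It models each specimen with biopsy protocol group as the explanatory variable, stratified by risk group. Group B is called the optical biopsy protocol. Section D defines yield on mucosal biopsy samples.

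**The concern.** A yield comparison can show the value of directing biopsies only if the read changes which tissue is taken or which tissue is counted. In the Group B procedure no sentence clearly lets the read add, withhold or move a biopsy, and in G2 no term separates read-positive from read-negative specimens. A perfect device and a useless one would then give nearly the same primary result.

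Two wrong conclusions become possible. A null result could be taken as evidence against directed biopsy, which was never tested. An arm difference could be credited to HRME when it came from the different 1 cm triggers. Aim 1b has the same problem: if both arms take the full set, the between-arm biopsy count cannot show a reduction. F2 also records a pre-HRME plan but describes no post-HRME plan to set beside it.

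**Working it through.** **1. The plan's own figure.** G1 expects 100 randomised, 15 to 20% non-completion and 40 per arm. 100 × (1 − 0.20) = 80, or 40 per arm, which reproduces at the 20% end (15% would leave 85). G1 gives no expected yield, effect size, biopsies per patient, correlation or power, so there is no power figure to check.

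**2. Site prevalence implied by the pilot.** Section C gives sensitivity 81%, specificity 85% and negative predictive value 95%, from "a small pilot study of HRME in a high risk BE population". Prevalence odds = 0.85 × 0.05 / (0.95 × 0.19) = 0.0425 / 0.1805 = 0.235, so prevalence = 19.1%. G2 expects few patients with neoplasia, so an assumed 5% is shown as well.

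**3. Expected yield under two readings of Group B.**

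| | Prevalence 19.1% | Prevalence 5% |
|---|---|---|
| Group A, all sites | 19.1% | 5% |
| Group B as written, all sites | 19.1% | 5% |
| Group B, read-positive sites only | 0.154 / (0.154 + 0.121) = 56% | 0.0405 / (0.0405 + 0.1425) = 22% |
| Share of sites read positive | 28% | 18% |

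The third row is the positive predictive value: 0.81p / [0.81p + 0.15(1 − p)].

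**4. Chance of a significant primary result.** Assumptions: 40 per arm, 12 sites per patient in both arms, beta-binomial neoplasia with intraclass correlation 0.2 to 0.4, independent false-positive reads, no stratification.
- As written: 4.0 to 5.6% with a cluster-robust t-test, and 4.3 to 5.5% with a random-intercept logistic model standing in for GLIMMIX. This is the type I error.
- Read-positive sites against all Group A sites: 98 to 100% at 19.1% and 46 to 70% at 5% (cluster-robust); 87 to 100% and 43 to 71% (random intercept).

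**5. If the targeted biopsies are extra read-positive samples.** Adding k to 12 gives (12 × 0.191 + 0.56k) / (12 + k) = 21.9% for k = 1 and 24.3% for k = 2. When the added sites keep each patient's own prevalence, the yield is 20.5 to 22.8% against 19.1%, and rejection is 6 to 13% (5 to 8% at 5% prevalence). The signal is heavily diluted.

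**6. The 1 cm triggers.** Assume 20% of patients raise suspicion of neoplasia short of high-grade dysplasia, with site prevalence 20% against 5% in the rest, and that Group A samples them twice as densely. Group A: (0.2 × 2 × 0.20 + 0.8 × 0.05) / (0.4 + 0.8) = 10%. Group B: 0.2 × 0.20 + 0.8 × 0.05 = 8%. The arms differ with no HRME effect.

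**7. What a directed strategy would cost.** Of 40 × 12 = 480 Group B sites, about 92 are neoplastic at 19.1% and 24 at 5%. A 19% miss rate leaves about 17 and 4 to 5 unsampled. Some 5 to 10% of patients with neoplasia would have none in a read-positive site.

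**8. What read-positive yield does not prove.** A device with 60% sensitivity and specificity still gives 0.114 / (0.114 + 0.324) = 26% against 19%. For visible lesions the read may only repeat white-light suspicion. With one lesion among 12 sites (half of such lesions neoplastic), flat prevalence is (2.29 − 0.5) / 11 = 16%. A read that calls every lesion positive and 15% of flat sites at random yields (0.5 + 0.15 × 11 × 0.16) / (1 + 1.65) = 29%.

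**The case against.** G2 is literally clear on the denominator: every biopsy counts. A reader might infer that the plan does not say which Group B specimens enter the analysis, but the documents do not support that. Section D limits yield to mucosal biopsy samples, and the Pathology text names resected specimens separately, so the EMR question is largely answered and needs only confirming. What stands is that counting every biopsy does not match the directed label.

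The Group B text is not wholly closed to direction. The targeted biopsies could be read as extra read-positive samples, although they follow from lesions that white light had already found. The suspicion of high-grade dysplasia that sets the spacing is not said to exclude the read, and the lesion reads come first. Aim 1b plainly expects that HRME may change the decision. This ambiguity is real, and it is a reason to state the rule.

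Biopsying every read site is also the right design for aim 2, which is unaffected.

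Finally, the site count, correlation and lesion figures are assumptions, and the simulation is unstratified although G2 stratifies. They affect the power figures in step 4. They do not affect the equality in step 3, which needs only equal sampling and equal prevalence in the two arms.

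**Conclusion.** This must be fixed. If the Group B procedure is followed as written, the primary contrast carries almost no information about HRME-directed biopsy: a yield ratio near 1.0 at any device accuracy, against about 2.9 (56% / 19.1%) or 4.4 (22.1% / 5%) if only read-positive sites counted. These ratios assume that pilot accuracy holds per site and that prevalence is equal across arms.

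Three stronger readings are tempting, and the documents do not support them.
- That rejection is exactly 5% whatever happens. The different 1 cm triggers can separate the arms without any HRME effect, so the 4 to 6% holds only under equal sampling.
- That aim 3 fails because no time saving can appear. The hope of a saving is in Section C. Aim 3 only compares times, and a longer Group B time is a valid answer.
- That endoscopists at different sites will follow different versions of Group B. G1 gives 47 local and 100 worldwide subjects while F1 selects a single-centre category. Neither shows how sites will behave.

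Nor does it follow that read-positive yield must replace the primary outcome. Set against Group A's unfiltered yield, it favours any better-than-chance device.

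**What to change.** 1. Reconcile Section D aim 1a, the F1/F2 arm definition and G2 with the Group B procedure, and reconcile the two 1 cm triggers. This review does not say which tissue should be taken.
2. If the full set is still taken, state in G2 that the all-biopsies contrast is not a test of directed biopsy, and confirm that EMR specimens are excluded, in line with Section D. Pre-specify a comparison within Group B of read-positive sites with the full set, using the reads recorded before biopsy. Report its yield, the biopsy count, the neoplastic sites and patients missed, and a flat-mucosa-only result. A between-arm directed yield is optional. If given, label it as the positive predictive value of the read and as not like-for-like with Group A.
3. For aim 1b, record a post-HRME plan beside the pre-HRME plan.
4. For aim 3, record biopsy time separately in Group B, as F2 already does in Group A.

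The cost is protocol and SAP wording, one plan field and one timing field, with no extra patients or biopsies. The drawbacks are overlap with the positive predictive value in aim 2 and low precision for flat mucosa if neoplasia is rare.
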